#### Table 3. Correlation evaluation table

Unlikely related	-	-	?	?		
Unrelated	-	-	-	-		
"+" indicates conformity, "-" indicates non-conformity, "?" Indicates unable to judge						

#### 14.1.5 Handing protocol of adverse events that may occur in this clinical trial

- (1) Pulmonary vascular injury: Accidental injury of pulmonary vessels during operation may cause massive hemorrhage, which is life-threatening. The reasons include ① anatomical variations; ② tight adhesions; ③ improper operation; ④ poor exposure. Once it occurs, the vessel rupture should be immediately compressed, but the force should be appropriate to avoid further injury. At this point, if the surgical field is not exposed enough, it should be enlarged. The proximal and distal ends of the ruptured vessels are then carefully dissected. After the distal vascular occlusion, the yarn ball can be removed, the hematocele can be sucked up. The rupture can be seen, and the continuous or bedding suture can be performed with atraumatic suture. Sometimes, the vessels are dissected and blocked from the pericardium. After pulmonary vascular injury, do not panic. Do not use common vascular clamp. You should ask experienced doctors on stage to help deal with. If the rupture is not large, 1 ~ 3 atraumatic Allis forces can be used to clamp quickly after sucking up the blood, and the rupture can also be directly sutured. It is not necessary to free the proximal and distal ends of the breach.
- (2) Pneumothorax: It occurs mostly in patients with bullae, and rupture of bullae causes pneumothorax. In patients undergoing extensive mediastinal lymphadenectomy, mediastinal pleural rupture can also lead to pneumothorax. After the occurrence of pneumothorax, pulmonary ventilation is more and more difficult. Finally respiratory insufficiency occurs, which is life-threatening. Once this complication is found during surgery, the gas in the pleural cavity should be immediately evacuated, or a chest drainage tube should be placed by expanding the mediastinal rupture. The incidence of this complication is low, with a rate of 0.8% reported in the literature.
- (3) Arrhythmia and myocardial ischemia: It mostly occur in patients with a history of heart disease, but no preoperative cardiac manifestations, intraoperative temporary physiological disorders can cause arrhythmia and myocardial ischemia. In order to prevent and reduce such complications, ① careful preoperative evaluation of cardiac function should be performed to prepare the population for medical or other treatment; ② some factors of cardiac dysfunction should be avoided during surgery, such as hypokalemia, hypovolemia, hypovolemia, tachycardia and acidosis, which should be corrected immediately once the above factors occur; ③ excessive extrusion and stimulation of the heart should not be performed during surgery. Once arrhythmia and myocardial ischemia are caused by extrusion or stimulation, the operation should be immediately stopped, and the operation should be continued after

the cardiac function recovers; ④ Conduct ECG monitoring during the surgery. Once arrhythmia and myocardial ischemia are found, the corresponding drug treatment should be rapidly given, and the cardiologist should be invited for assistance when necessary.

- (4) Postoperative intrathoracic hemorrhage: Patients with intrathoracic hemorrhage after pneumonectomy who are forced to re-enter the chest for hemostasis account for about 1% of pneumonectomy. The reasons include: ① Bleeding or oozing at the site of pleural adhesion transection, generally mostly at the top of the thoracic cavity; ② Bleeding after thoracic wall vascular injury, such as bleeding from the intercostal artery or internal thoracic artery. It is not easy to stop spontaneously because the bleeding comes from the systemic circulation with high pressure; ③ Pulmonary macrovascular injury, mostly resulted from loose ligatures, fierce blood loss, which is often too late to rescue. Treatment: In any of the following cases, early thoracotomy and hemostasis should be pursued without hesitation, and adequate amounts should be prepared to supplement hypovolemia.
- (5) Cardiac hernia: Cardiac hernia may occur after pericardiotomy or partial resection without suturing or repairing. This complication is rare, but dangerous, with a mortality rate as high as 50%. It occurs mostly after pneumonectomy, but the occurrence of cardiac hernias after lobectomy has also been reported. Typical clinical manifestations are sudden hypotension, tachycardia, and cyanosis. Causes are intrathoracic vacuum aspiration, endotracheal suctioning, severe cough, postural changes, and positive pressure ventilation. Diagnosis is extremely difficult, mainly based on vigilance and experience. Emergency chest X-ray is of great help in judging right hernia, and the heart can be seen to move from the original to the right side, but it is difficult to judge left hernia. Right hernia not only causes torsion of the superior chamber and vein, but also causes distortion and obstruction of the outflow tract. Left hernias are true strangulated hernias that can seriously affect filling and myocardial supply, and electrocardiograms may present with manifestations similar to myocardial infarction. Once the possibility of cardiac hernia is considered in clinical practice, the patient should be immediately placed on the healthy side, and individual patients have the possibility of cardiac repositioning. If the condition does not improve, bedside thoracotomy should be performed decisively for cardiac reduction and pericardial defect repair. There are various methods for the repair of right pericardial defects, including epicardial and pericardial fixation, artificial material or autologous tissue repair. Left pericardial defects may not be repaired if they extend down to the diaphragm.
- (6) Cardiac tamponade (cardiac tamponade): The pericardium is opened during pneumonectomy, and the treatment of bleeding point may be missed, resulting in blood accumulation in the pericardium. Hypotension, elevated central venous pressure, odd pulse, and heart failure may occur when hemopericardium reaches a certain degree. Ultrasound and radiography can confirm the diagnosis.

Treatment should rapidly drain the hemopericardium, open it from the original incision in the chest, or make an incision under the xiphoid process.

- (7) Arrhythmia: Arrhythmia often occurs after pneumonectomy in patients over 60 years of old. The incidence ranges from 20% to 30% after pneumonectomy and from 15% to 20% after lobectomy. Among all arrhythmias, atrial fibrillation is the most common, followed by sinus tachycardia, and atrial flutter, extrasystoles, nodal rhythm, chronic arrhythmias, and bigeminy may also occur. Paroxysmal atrial tachycardia with block, multifocal atrial tachycardia, tachycardia, sick sinus syndrome and atypical tachycardia are relatively rare. More than half of the arrhythmias events occur in the first 24 hours after surgery, with a peak period on postoperative Day 2 to 3. For the treatment of arrhythmia, the cause, such as improving hypoxia, appropriate sedation and analgesia, correcting water and electrolyte imbalance and maintaining acid-base balance, should be firstly removed. Then, depending on the type of arrhythmia, different drugs or other measures should be applied. Digitalis preparations can be used for tachyarrhythmias, and the general dosage for adults needs to reach 0.8 to 1.2 mg to be effective. Verapamil (verapamil) is effective in terminating tachyarrhythmias, with a slow intravenous bolus of 5 to 10 mg for the first time and repeated after 10 to 15 minutes if necessary. After the control of supraventricular arrhythmias, it is changed to verapamil orally (40~80 mg/time, 3 times/day) for maintenance. For atrial arrhythmias that fail to respond to medical treatment and have hemodynamic disturbances, synchronous direct current cardioversion should be used. The first choice for drug treatment of tachycardia is lidocaine (50~100 mg, intravenous bolus), followed by continuous intravenous infusion maintenance at  $1 \sim 2$  mg/min. Bradycardia may be treated with atropine or intravenous isoproterenol. When third-degree atrioventricular block or sick sinus syndrome occurs, the installation of artificial cardiac pacemaker should be considered.
- (8) Myocardial ischemia and myocardial infarction: The incidence of silent myocardial ischemia after pneumonectomy is about 3.8%. Patients with coronary heart disease and myocardial infarction are prone to experience this situation, which often occurs on the 2nd to 4th day after surgery. Therefore, close cardiac monitoring should be performed after pneumonectomy. Once diagnosed, enteric-coated aspirin (160 to 325 mg/day) may be given. Some beta blockers are used appropriately to prevent myocardial infarction and death. The incidence of myocardial infarction after pneumonectomy is about 1.2%, and patients with preoperative diagnosis of coronary heart disease are prone to experience this situation, with a mortality rate as high as 50% to 75%. Once the diagnosis is confirmed, the cardiology consultation should be urgently requested to assist in treatment.
- (9) Orthostatic hypoxemia: After pneumonectomy or lobectomy (usually right upper lobe or right upper lobe and middle lobe), the patient has no or slight dyspnea in supine position, and the saturation is normal or

slightly lower than normal. However, when the patient sits up or stands up, the dyspnea or dyspnea is aggravated, and the saturation becomes abnormal or further decreased. This is called "orthostatic hypoxemia".

- (10)Pulmonary edema after pneumonectomy: Pulmonary edema after pneumonectomy, especially after right pneumonectomy, should be diagnosed if progressive dyspnea, cyanosis, tachycardia and dysphoria, pink foamy sputum and moist rales in the lungs occur. Although the incidence is not high (about 2% to 5%), the mortality rate is high (7% to 80%). The mechanism of this complication is not very clear, but clinical observations and experiments have demonstrated that excessive perioperative fluid infusion is an important cause. As fluid filtered out of the pulmonary capillaries exceeds the capacity for lymphatic reflux, fluid begins to accumulate in the peribronchiolar space. The lungs become stiff, and the work of breathing increases. When the peribronchial space is completely filled with water, the alveoli are also quickly affected, so hypoxemia or even death occurs. The treatment includes oxygen inhalation, fluid restriction, application of morphine and diuretics. In severe cases, endotracheal intubation and mechanical respiration should be performed again with PEEP ventilation mode.
- (11)Respiratory insufficiency: Incision pain, chest wall activity limitation, cough and weakness, airway secretion retention after pneumonectomy may cause atelectasis and inflammation, coupled with flatulence and other factors will cause respiratory insufficiency, manifested as shortness of breath, difficulty, rapid pulse, restlessness, elderly patients and even confusion. Blood gas tests show a decrease in PO2 and PCO2 in the early stage, followed by an increase in PCO2. Chest X-ray shows partial or total atelectasis of the remaining lungs. Once this disease is suspected, secretions in the airway should be immediately removed in addition to oxygen inhalation. If fiberoptic bronchoscopy suction does not work, tracheotomy should be considered and mechanical breathing should be performed if necessary. This complication often occurs in people with poor lung function. Therefore, pulmonary function assessment is very important. Antibiotics, bronchodilators, smoking cessation, chest physiotherapy, postural drainage and appropriate exercise can improve pulmonary function and reduce the occurrence of postoperative respiratory insufficiency.
- (12)Massive atelectasis: The incidence of massive and severe atelectasis after lobectomy has been reported to be about 7.8%, and the incidence after right upper or right upper middle lung resection is higher than that after right lower or left lobectomy (15.5%, 6%). Patients present with shortness of breath, varying degrees of cyanosis, shortness of breath, accelerated heart rate, and even high fever. Careful physical examination and chest X-ray can help in the diagnosis. Once the diagnosis is confirmed, tracheal and bronchial aspiration and lavage should be performed immediately.
- (13)Lobar torsion and gangrene: Lobar rotation of 180° or more along the bronchovascular pedicle, called

lobar torsion, is mostly caused by excessive intraoperative traction and inversion of the lobe. In addition, if the oblique and horizontal fissures are fully developed, the right middle lobe is prone to torsion after resection of the right upper lobe or right lower lobe. After lung lobe torsion, it causes vascular occlusion, which in turn causes pulmonary infarction and pulmonary gangrene. Once this disease is suspected, the chest should be opened immediately. If the twisted lobe remains viable, it can be reduced and fixed in its normal position. Otherwise, lobectomy should be performed.

- (14)Pulmonary infarction after pulmonary angioplasty: Patients who require pulmonary angioplasty at the same time for lobectomy or bronchial sleeve lobectomy may have thrombosis due to angulated bending or stenosis of pulmonary vessels after surgery, thus causing pulmonary infarction. Patients have low-grade fever, increased density of the lung parenchyma on chest X-ray, and no bronchial obstruction or stenosis can be seen on fiberoptic bronchoscopy. The bronchial mucosa is initially normal and later becomes congested, edematous, and cyanotic. Pulmonary angiography or pulmonary perfusion scan can help in the diagnosis. Once the diagnosis is established, the remaining pneumonectomy should be performed.
- (15)Postoperative pneumonia: The occurrence of pneumonia is closely related to airway secretion retention and atelectasis. The incidence of postoperative pneumonia is 7% in lobectomy and 6.6% in pneumonectomy, respectively. Aspiration pneumonia most commonly occurs in patients with bronchopleural fistula. The condition is prone to develop acute respiratory distress syndrome, and the mortality rate can be 40%. Patients accepting postoperative mechanical respiratory assistance also often suffer from pneumonia. Most pneumonias are caused by bacteria, while viruses, fungi, and mycoplasmas may also be pathogens. In treatment, it is mainly based on the antibiotics application, nutritional support and respiratory tract management.
- (16)Prolonged air leak: Air leaks from the rough surface of the lung after lobectomy or segmentectomy are common. With the expansion of the remaining lung and the elimination of the residual cavity, air leakage generally stops 2 to 3 days after surgery. If there is still air leakage more than 7 days after surgery, it is called "prolonged air leakage". The incidence after pneumonectomy is 15.2%. Although prolonged air leaks rarely cause other complications, the length of hospital stay will be prolonged by 5 to 6 days. The management of prolonged air leaks varies according to the condition, while the experience of thoracic surgeons also plays a significant role, with no single and fixed treatment mode. Increase or decrease the attraction force of closed thoracic drainage system, and install another thoracic drainage tube. Use medical glue to block the small bronchi of air leaking lung segment. Spraying fibrin glue on the rough surface of lung or spraying talc on thoracic cavity can be applied. The second thoracotomy is rarely require. However, if there is an infection in the thoracic cavity and there is a lot of air leakage,

bronchopleural fistula may occur. After the diagnosis of bronchopleural fistula is confirmed, reoperation is required.

- (17)Bronchopleural fistula: The incidence of bronchopleural fistula after pneumonectomy or lobectomy ranges from 1% to 4%. Residual tumor at the bronchial stump, preoperative radiotherapy, diabetes, positive sputum for pulmonary tuberculosis, and right pneumonectomy are high risk factors for the development of fistulas. Closed thoracic drainage should be performed promptly after the diagnosis of bronchopleural fistula, and systemic antibiotics should be given. Before closed thoracic drainage, the patient should be kept in the affected lateral decubitus position to prevent intrathoracic effusion from filling into the lung. Patients with small fistulas (about 3 mm) have the possibility of self-healing after closed drainage. Fibrin glue injection via fiberoptic bronchoscopy can promote the healing of small fistulas. In patients with large fistulas, reoperation may be considered within 7 days after surgery. The bronchial stump may be resutured, embedded with muscle flap, pericardium, or greater omentum, and lavage with postoperative thoracic antibiotic solution to make it sterile. Bronchopleural fistulas more than 7 days are mostly associated with severe thoracic infection and are no longer suitable for re-suturing of the broken end, and thoracic fenestration should be performed 2 weeks after closed thoracic drainage when the mediastinum has been fixed. Fistulas can heal in 30% of patients after fenestration. If the fistula is not healed, thoracoplasty or exposure of the main bronchus through a midline incision should be taken into consideration, which is cut and closed at the root of the main bronchus. Bronchopleural fistula after lobectomy is sometimes solved by total resection of the remaining lung.
- (18)Persistent residual cavities: After lobectomy, especially in the elderly, persistent residual cavities often appear in the pleural space, most of which are located at the top of the chest and a few above the diaphragm. Most postoperative residual cavities are asymptomatic, and disappear after a few months with expansion of the remaining lung, rise of the diaphragm, displacement of the mediastinum, collapse of the chest wall, and organization of residual pleural fluid. Therefore, no special treatment is required. A small number of patients with residual cavity infection, and even complicated by bronchopleural fistula, will present with symptoms. They should be treated as empyema and bronchopleural fistula. It is estimated that residual cavities will occur after surgery, especially after upper lobectomy. The parietal pleura can be dissected to form a tent to convert the intrapleural residual cavity into extrapleural.
- (19)Pleural effusion: After lobectomy or smaller lung resection, it is common to have a small amount of effusion at the bottom of the chest. Over time, the effusion gradually absorbs and organizes and may not be treated. However, when a large amount of effusion occurs, the cause should be identified. Thoracentesis should be performed or closed drainage should be installed again. Otherwise, there will be effusion infection and consequences affecting lung function.

- (20)Empyema: The incidence is 1% to 3%. Empyema may occur simultaneously with bronchopleural fistula or alone. Intraoperative thoracic contamination, secondary thoracotomy for hemostasis or repair of bronchial fistula, and postoperative mechanical respiration are risk factors for concurrent empyema. Clinically, the patient is febrile, with toxic symptoms, increased white blood cell count, and elevated C-reactive protein levels. The diagnosis can be established by evacuation of pus by thoracentesis. Once the diagnosis of empyema is established, a series of measures for the treatment of empyema, such as thoracic drainage and the use of antibiotics, should be taken immediately.
- (21)Chylothorax: Chylothorax after pneumonectomy is rare, with an incidence of about 0.05% to 0.74%. If the thoracic duct is injured during pneumonectomy, or the lymphatic vessels connect the mediastinal lymph nodes and thoracic duct, or the lymphatic vessels of the lung, this disease may occur after surgery. Chylothorax may complicate left or right, lobar or total, upper or lower lobectomy. Chylothorax after lobectomy is mainly characterized by pleural fluid becoming milk-like after eating and increased pleural fluid drainage. Chylothorax after pneumonectomy is characterized by increased pleural effusion, mediastinal displacement, dyspnea, and even decreased blood pressure. Milk-like fluid can be aspirated by thoracentesis. Lymphangiography can be done in conditional hospitals, either to show thoracic duct fistulas or not. Those who do not show a fistula are often cured conservatively. Once the diagnosis of chylothorax is established, fasting, intravenous nutritional support, and maintenance of patent thoracic drainage should be performed immediately. In patients with lobectomy is unlikely, and if the daily pleural fluid exceeds 300 mL, low thoracic duct ligation should be performed by thoracotomy, or closure with fibrin glue. The daily drainage fluid of chylothorax after lobectomy and then thoracotomy is more than 500ml.
- (22)Esophageal injury: When pneumonectomy is performed for pulmonary inflammatory lesions or lung cancer, if mediastinal anatomy and mobilization are difficult, it may damage the esophagus, with an incidence of 0.5% reported in the literature, and more than 90% events occur on the right side. Preoperative gastric tube placement may reduce the chance of esophageal injury. When esophageal injury is suspected intraoperatively, air or methylene blue can be injected into the esophagus. Once the diagnosis is confirmed, it should be repaired immediately. If missed diagnosis occurs during surgery, mediastinal infection and empyema will occur after surgery.
- (23) Wound infection and wound dehiscence: Wound infection and dehiscence after pneumonectomy are relatively rare. In case of incision infection, there are corresponding symptoms and signs, and antibiotics should be drained and used in time. Early incision dehiscence can be sutured again; late dehiscence, mostly as a result of infection, should be debrided, drained, and sutured after infection control.

- (24)Subcutaneous emphysema: The residual gas in the pleural cavity after pneumonectomy can enter the soft tissue of the chest wall through an intercostal incision when the patient changes position or coughs, forming subcutaneous emphysema. If there is no bronchopleural fistula, the subcutaneous emphysema is mild and confined to the vicinity of the incision. No special measures are generally taken.
- (25)Phrenic and recurrent laryngeal nerve injury: When lung cancer or metastatic lymph nodes invade the phrenic nerve, the phrenic nerve has to be cut or removed to remove the tumor, which is the most common cause of pulmonary resection complicated by phrenic nerve injury. This was followed by severe adhesions on the separated mediastinal surface as well as phrenic nerve injury when clamping or coagulation of bleeding points near the phrenic nerve. Phrenic nerve injury affects the ventilatory function of patients, and special care should be taken for those with marginal pulmonary function.
- (26) Spinal cord injury: During pneumonectomy, if there is bleeding from the spinal costal horns, blood may flow into the spinal canal, causing spinal cord compression and paraplegia. If bleeding is controlled with hemostatic materials, these materials have the potential to slip into the spinal canal to compress the spinal cord. If bleeding continues at the spinal costal angle, neurosurgeons should be asked to help enlarge the hole and stop bleeding and oozing with bipolar electrocautery and other special methods.
- (27) Dura mater tear arachnoid pleural fistula: This complication often occurs during lung cancer surgery. When the tumor invades the posterior chest wall and spinal costal angle, it may tear the dura mater during separation, resulting in arachnoid pleural fistula, or cerebrospinal fluid leakage. During pneumonectomy. If clear fluid is found to flow out from the posterior end of the incision and near the spino-costal angle, this disease should be highly suspected, and neurosurgeons should be consulted to enlarge the foramen, or another laminectomy should be performed to directly suture the dural cleft. If this disease is not found during surgery, it is not easy to confirm the diagnosis in the early postoperative period because cerebrospinal fluid mixed in the blood is not easy to identify. The possibility of this complication should be vigilant when there are gradually less blood components in the pleural fluid and the pleural fluid becomes clear, while the total amount is still many. Cranial copy and CT can show pneumocephalus, and radionuclide myelography can further help in the diagnosis. Neurosurgical consultation should be requested as early as possible after the diagnosis is confirmed. Although some cases can heal spontaneously, preparation should be made for posterior laminectomy. Patients with cerebrospinal fluid leakage may be asymptomatic, but also may be with symptoms, such as headache, seizures, mental status changes, meningeal irritation. There are even death cases reported. Bacterial meningitis is rare.
- (28)Peritumoral vascular embolism: Tumor emboli can be detached from the pulmonary veins and flow into branch vessels of the aortic arch and femoral arteries. Some other embolized vessels reported in the

literature are the cerebral, upper extremity, and mesenteric arteries. 84% of embolizations are caused by surgery, 16% are spontaneous, and the mortality rate is as high as 50%. When possible, embolectomy should be performed. The method of intraoperative prophylaxis is mobilization, ligation, and transection of the pulmonary veins at the proximal end of the intrapericardial tumor thrombus, and if necessary, resection of a small portion of the left atrium.

- (29)Pulmonary embolism: The incidence of pulmonary embolism after pneumonectomy ranges from 1% to 5%. Most emboli originate from veins in the lower extremities or pelvis, and a small proportion from the pulmonary artery stump. The pulmonary artery stump is prone to thrombus formation due to its ruffling and blind tubular shape, where blood slowly swirls. Right embolization after pneumonectomy is rare because of the stump of the right pulmonary artery. The mortality rate of pulmonary embolism is as high as 50%, often with sudden onset and death. Lower limb infusion should be avoided. Patients are encouraged for early physical activities. Pulmonary artery treatment with stapler can reduce the occurrence of this complication.
- (30)Deep Vein Thrombosis: Ziomek et al. (1993) reported this complication. Of the 77 patients with lung cancer, 4 had preoperative deep vein thrombosis and 11 had postoperative deep vein thrombosis, for an overall incidence of 19%. Of the 17 patients who received preoperative oral aspirin or ibuprofen, none developed thrombosis after surgery, and it was considered that patients with adenocarcinoma, large tumors, late TNM stage and relatively large surgery were prone to deep venous thrombosis and embolism.
- (31)Renal failure: Renal failure after pneumonectomy is rare. However, 197 cases of pneumonectomy have been reported. Renal failure occurs in 15% of patients after operation. The elderly over 70 years old are an important cause of postoperative death.
- (32)Cerebrovascular accident: For patients with lung cancer, a distinction should be made between a true "stroke" or a "brain metastasis" that is not diagnosed preoperatively. CT and MRI can help differentiate.
- (33)Gastrointestinal bleeding: Gastrointestinal bleeding after pneumonectomy is rare, often accompanied by other fatal complications (e.g., severe respiratory failure, sepsis, etc.), which mostly manifests before the end of life.
- (34)Pyogenic empyema: After pneumonectomy, the chest residual cavity can be infected and form empyema. Bacteria come via blood from other parts of the body, or from insidious bronchopleural fistulas. The clinical presentation of this complication is not obvious at the beginning, and typical symptoms and signs of empyema appear later.
- (35)Hemorrhagic empyema: It has been reported in the literature that several years after pneumonectomy, a gradually growing hematoma appears in the thoracic stump with blood from granulation tissue in the

stump. Hematomas can cause mediastinal displacement and compression of the unaffected lung. Re-operation to remove the hematoma can cure this disease.

- (36)Fungal empyema: Late fungal empyema after pneumonectomy is mostly caused by Aspergillus fumigatus. In treatment, the best way is thoracoplasty. Open drainage should not be advocated because reoperation, such as muscle flap packing or thoracoplasty, is also required after open drainage.
- (37)Device-related adverse event: The test device may cut to nerves and great vessels during use. The inability to deploy or retract the reload may occur during the deployment of the reload. There may also be battery or motor failures that render the device inoperable. In such cases, the necessary treatment should be performed according to the actual situation, such as conversion to thoracotomy or device replacement.

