#### (7) Incidence of device defects

**Definition:** An test device defect that occurs during the course of a clinical trial. "Staple pop" due to human factors (e.g., incorrect reload selection) is not a defect of the device.

Measurement time: During the whole process of clinical trial.

**Calculation formula:** Incidence of device defect = number of device defects/total number of devices  $\times$  100%.

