#### 14.1.1 Definition of adverse events

Adverse event (AE): refers to any adverse medical event occurring in the clinical trial process, no matter whether it is related to the investigational medical device or not.

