#### 14.1.6 Handing of adverse events that may occur in this clinical trial

The above are foreseeable adverse events of this study. However, when the subjects suffer from adverse events, the investigators may treat adverse events according to clinical diagnosis and treatment regulations as needed and record them faithfully.

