## 14.3 Reporting and Handling of Device Defects

Device defects refer to unreasonable risks that may endanger human health and life safety under normal use of a medical device during a clinical trial, such as labeling errors, quality problems and failures, etc.

Possible device defects: identification error, product quality problem; design defect; damage of disinfection package, etc.

All device defects are documented on the Device Defect Record form, and device defects that could have led to serious adverse events shall be reported and documented within 5 working days.

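### Section 14.1.5(37) lists stapler malfunctions as adverse events even when nobody is harmed, against the medical-event definition in 14.1.1 and 8.1.8(6), so the compared AE rate is ambiguous

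*Combined protocol and SAP*

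**What the plan says.** Section 14.1.5 lists foreseeable events and how to handle them. Item (37) opens: "Device-related adverse event: The test device may cut to nerves and great vessels during use". It goes on to failure to deploy or retract the reload, and then: "There may also be battery or motor failures that render the device inoperable". Replacing the device is one of the responses it names, so it covers a malfunction that ends with a swap and no effect on the subject. Section 14.1.6 closes the list: "The above are foreseeable adverse events of this study". Section 14.1.3 sends every adverse event to the adverse event column of the CRF, with a severity.

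The definition in 14.1.1 is narrower. An adverse event "refers to any adverse medical event occurring in the clinical trial process". Section 8.1.8(6), which defines the compared AE incidence, likewise speaks of an untoward medical occurrence. The three severity grades in 14.1.2 are all described by symptoms.

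Section 14.3 defines device defects by examples, "such as labeling errors, quality problems and failures, etc", and puts all of them on a Device Defect Record form. Section 14.2.2(4) names serious adverse events and device defects as separate things.

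Under 9.5 and 9.7.1, AE incidence and device defect incidence are both safety indicators, tested between groups at 0.05.

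**The concern.** No section says whether a malfunction with no medical consequence is an adverse event, a device defect or both. A site that follows 14.1.5(37) and 14.1.6 enters it in the AE column. A site that follows 14.1.1 does not. The AE numerator therefore depends on which section the investigator reads, at five sites where investigators know the arm (8.2.4).

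Item (37) also names only the test device, and 8.2.4 uses that term in contrast to the control device. A literal reader could log malfunctions as AEs in the test arm and not in the control arm. The AE comparison could then move with no medical difference between the arms, or with no difference in malfunctions either. In a registration trial of a powered stapler, AE incidence is one of the safety results that will be read closely.

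**Working it through.** **Step 1. One event under each section.** Suppose the motor of the allocated stapler stops, the stapler is exchanged, and the subject has no consequence.

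| Section | Classification |
|---|---|
| 14.1.5(37) with 14.1.6 | Adverse event; no harm required |
| 14.1.3 | As an AE, goes in the CRF column with a severity |
| 14.1.1 and 8.1.8(6) | Not an adverse event; nothing medical occurred |
| 14.1.2 | Cannot be graded; there are no symptoms |
| 14.3 | Device defect; it is a failure |

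The first row contradicts the third. The second and fourth cannot both be met. The last is compatible with either reading of the AE rules.

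**Step 2. Inputs for size.** The group size is the plan's own. Section 9.2.1 uses 97% success in both groups, a 10-point margin, one-sided 0.025 and 80% power:

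- n = 2 x 0.97 x 0.03 x (1.960 + 0.842)^2 / 0.10^2 = 45.7
- the plan's correction, (n/4) x [1 + sqrt(1 + 4/(0.1n))]^2 = 64.1, so 65
- 65 / 0.8 = 81.25, so 82 per group and 164 in total

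This reproduces 65, 82 and 164.

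The documents give no AE rate and no malfunction rate, so these are assumed:

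- background AE rate a (any medical AE), the same in both arms: 20% to 80%
- subjects with a harmless malfunction counted as an AE: 5% or 10% in the test arm (mT) and 2% in the control arm (mC)
- malfunctions independent of other AEs
- 82 analysed per group, two-sided Fisher test at 0.05 (9.7.1 allows Pearson or Fisher)

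**Step 3. Formula.** The recorded AE rate in an arm is 1 - (1 - a)(1 - m). The difference between arms is (1 - a)(mT - mC). For example, with a = 20%, mT = 10% and mC = 2%, the rates are 1 - 0.80 x 0.90 = 28.0% and 1 - 0.80 x 0.98 = 21.6%, a difference of 6.4 points. The chance of p <= 0.05 is the sum of the two binomial probabilities over the Fisher rejection region.

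| Background AE rate | No malfunctions counted: chance | 5% v 2%: shift, chance | 10% v 2%: shift, chance |
|---|---|---|---|
| 20% | 3.1% | 2.4 points, 4.3% | 6.4 points, 11.8% |
| 40% | 3.3% | 1.8 points, 3.8% | 4.8 points, 6.9% |
| 60% | 3.3% | 1.2 points, 3.5% | 3.2 points, 4.9% |
| 80% | 3.1% | 0.6 points, 3.1% | 1.6 points, 3.6% |

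**Step 4. The test-arm-only reading.** If control-arm malfunctions are never entered as AEs, mC is 0 and the shift is (1 - a) x mT, whatever the true control malfunction rate. For mT of 5% to 10% and the same background rates, that is 0.20 x 5 = 1.0 point up to 0.80 x 10 = 8.0 points. By the same exact method the chance of p <= 0.05 is about 3% to 17%.

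**The case against.** The best reply is that 14.1.5 is a handling list, not a counting rule. The counted indicator is defined in 8.1.8(6) as a medical occurrence, and a careful investigator would apply that. This has force, but 14.1.6 calls the whole list adverse events and 14.1.3 sends every adverse event to the CRF. The text gives a site good grounds to count a harmless malfunction.

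A second reply is that the effect is small. This largely stands. Most cells of the table stay below the nominal 5%, and at 5% v 2% nothing exceeds 4.3%.

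A third is that AEs and defects are listed under 9.7.1, so each event's nature would be visible. That helps a reader of the report, but a listing shows events as coded and does not make the tested rate consistent across sites.

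Three stronger readings are tempting, and the documents do not support them.

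- A reader might infer that the device defect rate is equally ill-defined, or diluted by label and package faults. Section 14.3 counts failures as defects whatever item (37) says, and covering several kinds of fault is breadth, not contradiction. Function in use is already recorded under 8.1.9 (firing, repeated firing, battery supply) and tested between groups under 9.7.1, so a defect indicator confined to failures in use is a design preference.
- A reader might infer that investigators may choose the AE form instead of the defect form. Section 14.3 requires every defect on the defect form, 22.2(13) requires all AEs and defects to be recorded, and nothing makes the two exclusive. A failure entered only as an AE would breach 14.3.
- A reader might want a power figure for the defect comparison. Section 8.1.8(7) sets "Incidence of device defect = number of device defects/total number of devices", and the number of devices per arm is not given, so a calculation on 82 subjects per group would not describe that comparison.

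**Conclusion.** The contradiction is in the text. Section 14.1.5(37), confirmed by 14.1.6, makes a malfunction without harm an adverse event. Sections 14.1.1 and 8.1.8(6) do not, and 14.3 treats the same event as a device defect. The consequence is confined to the AE incidence compared at 0.05, which may take in non-medical events, possibly from one arm only and unevenly by site.

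The effect is modest and rests on assumed rates. With malfunctions in 5-10% v 2% of subjects and background AE rates of 20-80%, the chance of p <= 0.05 is about 3-12%, against about 3% otherwise. It reaches about 17% only if malfunctions occur in 10% of test subjects, none are entered for controls, and the background AE rate is 20%. A reader might also infer that the main conclusion is at risk. It is not: the non-inferiority criterion in 9.5 rests on the cutting and anastomosis success rate, and neither that endpoint nor the sample size depends on how malfunctions are coded.

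**What to change.** Reconcile 14.1.5(37) and 14.1.6 with 14.1.1 and 14.3. State that a malfunction of the allocated stapler or reload, in either arm, is recorded as a device defect under 14.3. State that it is also an adverse event only if the subject has an untoward medical occurrence, and that the two records are then linked. Replace the reference to the test device in item (37) with wording that covers both arms. Section 8.1.8(7) also speaks of a test device defect, so the same wording belongs there.

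The cost is a few sentences and a cross-reference between two forms, with no extra subjects or procedures. This protocol version is dated 25 March 2019 and the last subject was due to finish in March 2019. If data collection is over, the rule can go into the SAP, which 9.1 says is finalised before database lock, and be applied at the blinded data review mentioned in 8.1.3(4). Tabulating defects by type in the listing is optional.
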